	6.6	Study Schematic	g
	6.7	Study Activities	10
7	Stuc	ly Objectives and endpoints	10
	7.1	Primary Objective	10
	7.2	Secondary Objectives	10
	7.3	Endpoints	10
8	Inve	stigational Plan	11
	8.1	Overall Study Design	11
	8.2.2 8.2.2 8.2.2 8.2.2 8.2.2	Pirst visit Subsequent visits Salar Early Study Termination Salar Early Salar Early Study Termination Salar Early	11 11 11
9	Sele	ction of Subjects	12

	9.1	Selection of Study Population	12
	9.2	Inclusion Criteria	12
	9.3	Exclusion Criteria	12
	9.4	Contraception/Pregnancy Avoidance	12
10	Stud	ly Assessments and Procedures	13
	10.1	Study Assessments	13
	10.1	•	
	10.1		
	10.1	.3 Subsequent visits	13
	10.2	Assessment Types	
	10.2	·	
	10.2	,	
	10.2 10.2		
	10.2	, ,	
	10.2		
	10.2		
	10.2		
1 1	Data	Collection and Management	15
	11.1	Monitoring	15
	11.2	Data Collection	15
	11.3	Database Management and Quality Control	15
	11.4	Statistical Considerations and Data Analysis	16
12	Ethic	cal Considerations	16
	12.1	Ethical conduct of the study	16
	12.1	.1 Declaration of Helsinki	16
	12.1	.2 Ethics Committee	16
	12.2	Informed Consent	16
	12.3	Patient and Study Data Protection	16
	12.4	Subject Identification	16
	12.5	Conflict of Interest	17
13	Fina	nce and Insurance	17
14	Repo	orting and Dissemination	17
15	Con	flict of interest statement	17
16	Dofo	rances	17

2 Trial Registration/Protocol Summary

Information	
EudraCT number:	
Date of registration:	
Clinical Trial	
Authorization (CTA)	
, ,	
from FAMHP (FAGG)	
Date of approval:	
ClinicalTrials.gov:	
Official Title:	An prospective exploratory study on the value of bio-electrical impedance analysis in IBS.
Study Phase/Type:	
Condition:	IBS
Objectives:	The primary objective is to compare the BIA parameters including physical angle (PhA) between IBS and healthy individuals. The secondary objectives are double: - Correlation of PhA with different parameters implicated in IBS pathophysiology in IBS patients and healthy subjects. - Evolution of PhA according to response to therapy.
Investigational Prod-	None
uct: Interventions:	Pio electrical impedance analysis questionnaires
	Bio-electrical impedance analysis, questionnaires
Endpoints:	The primary endpoint of this study is to explore whether PhA differs between IBS patients and healthy volunteers at visit 1.
	The secondary endpoints are divided in two parts.
	The first part explores correlations at initial presentation among IBS
	patients and healthy subjects:
	- Correlation of PhA with IPAQ
	 Multiple regression of IBS status with multiple independent variables (PhA, IPAQ, dietary and FODMAP intake, psychological variables, gender) Differences in fecal microbiome between groups
	In the second part, we want to explore changes of PhA according to
	changes in IBS-SSS in IBS patients only.
Study population:	IBS patients
Number of patients:	20 IBS patients and 20 healthy subjects
Overview of	Prospective exploratory study
study design:	
Statistical	
Considerations:	
	Dref [name]
Sponsor:	[name]. [name]
Country(ies) of	Belgium
Recruitment:	
Inclusion Criteria:	IBS patients:
	- Patients aged 18 - 75 years; - Fulfilling the ROME IV criteria for IBS;
	For healthy volunteers:
	- Patients aged 18 - 75 years;
Exclusion Criteria:	 Clinical suspicion of an organic disorder different from IBS (patients can be included when this disorder had been excluded); Known inflammatory bowel disorder;
	- Known major intestinal motility disorder;

	 Alcohol (defined as more than 14 U per week) or other substance abuse; Active psychiatric disorder; Known systemic or auto-immune disorder with implication for the GI system; Prior abdominal surgery (with the exception of cholecystectomy or appendectomy); Any prior diagnosis of cancer other than basocellular carcinoma; Current chemotherapy; History of gastro-enteritis in the past 12 weeks; Dietary supplements unless taken at a stable dose for more than 12 weeks; Treatment with neuromodulators (one neuromodulator taken at a stable dose for more than 12 weeks is allowed); Pregnancy.
Date of first	
enrolment:	
Target sample size:	20 IBS patients and 20 healthy subjects

3 Protocol Version History

Version No.	Approval Date Lead EC	Release Date

4 Sponsor/Coordinating Investigator Information

Coordinating Investigator [name]. [name]

Sponsor

Principal Investigator [name]. [name]

Co-investigators

Additional co-researchers

Statistician Laboratory (ies) Pharmacy

Study Coordinator [name] - [name]

Study sites and co-investigators

5 List of Abbreviations

4dFD Four Day Food Diary

BIA Bio-electrical Impedance Analysis

FODMAP Fructo, oligo-, di-, polysacchardies and polyols

HRV Heart Rate Variability
IBS Irritable Bowel Syndrome
IBS-SSS IBS-Symptom Severity Scale

IPAQ Internation Physical Activity Questionnaire

6 Introduction

6.1 Overview of Disease Pathogenesis

In many aspects, irritable bowel syndrome (IBS) remains a mystery. According to the Rome IV consensus, it is defined as abdominal pain for 3 days a week present since at least 3 months with onset at least 6 months earlier (Lacy 2016). The abdominal pain needs to be associated with two of the following: change in stool form, change in stool frequency or associated with defecation. The aetiology as well as the pathophysiology are uncertain. Studies attribute a role to prior infection, low-grade inflammation, genetic susceptibility, psychological influences and disturbances of the brain-gut axis. As a result of the unclear pathophysiology, a multitude of therapeutic interventions are available, varying from promotion of a healthy lifestyle, dietary modifications, treatments targeting the gut microbiome, antispasmodics, prokinetic or anti-kinetic treatments as well as psychological interventions.

All guidelines recommend lifestyle modifications with increased physical activity, when treating IBS. While the beneficial effects of increased physical exercise have been demonstrated (Johannesson 2011), research on the underlying mechanisms underlying this positive effect remain scarce. Dietary modifications, changes in the gut microbiome (Claus 2021), improved intestinal barrier function (Dalton 2019, Pasini 2019), decreased stress response (Caplin 2021), increased vagal tone (Bonaz 2016), improved mental well-being (Hale 2021, Grocke-Dewey 2021) have been proposed. Further complicating this equation, endurance athletes also report IBS-like symptoms (Killian 2019). However, it remains unknown whether the same pathophysiology is involved as compared to IBS patients with a sedentary lifestyle. Increased intestinal permeability has been implicated.

Apart from the uncertainties about the pathophysiological mechanisms, the absence of an objective marker to diagnose or to follow-up the evolution of IBS represents a major drawback in IBS research. Diagnosis of IBS largely relies on the clinical symptoms and absence of alarm features. No diagnostic test confirms or refutes the diagnosis. Moreover, response to therapy is measured as the improvement of symptoms, which is again susceptible to subjective interpretation by the subject. Current research focuses on different candidate markers (Nakov 2021) such as volatile organic compounds, faecal or serum biomarkers.

Phase Angle (PhA) is a new marker for body cell mass and frailty, derived from Bioelectrical Impedance Analysis (BIA). It has been shown to provide insight into the muscle mass in health and disease at different age (Marini 2012, Rodriguez-Rodriguez 2016, Zanforlini 2019). PhA is considered a potential marker of oxidative and inflammatory processes (da Silva 2022). More recently, its role as a screening tool for physical fitness in obese adults was demonstrated (Streb 2020). Considering the putative role of physical inactivity, dietary factors such as Fructo-, oligo-, di-, polysaccharides and polyols (FODMAP) and low grade inflammation in IBS symptoms as well as physical fitness, PhA might act as a marker for the disease and/ or its evolution during treatment.

6.2 Epidemiology

Up to 5% of the worldwide population suffers from IBS when diagnosed based on the Rome IV criteria. This number increases even more when applying the Rome III criteria, as this diagnosis doesn't restrict the cardinal symptom to abdominal pain, but also allows for abdominal discomfort. On the other hand, a sedentary lifestyle is frequently observed in Western countries. Physical inactivity has been associated with major conditions including obesity, atherosclerosis, non-alcoholic fatty liver disease and diabetes, and might as well be implicated in the pathophysiology of IBS.

6.3 Current Treatments

Current treatment of IBS can be broadly divided into lifestyle modifications, dietary interventions, medical treatment and non-pharmaceutical psychological interventions, including cognitive behavioral therapy. Despite the fact that lifestyle modifications are included in virtually all guidelines, research in the role of physical activity remains underassessed as compared to the other interventions.

6.4 Study Rationale and Purpose

The study aim is to investigate the BIA parameters in general, and PhA in particular in IBS patients and to compare these with values from healthy controls, while assessing the relationship with other confounding parameters in IBS: psychological parameters, physical activity, dietary pattern (with

[figure not shown]
special interest in FODMAP intake). In a second phase, the evolution of the BIA parameters will be analyzed according to response to therapy.

6.5 Rationale for Study Design

The role and significance of bio-electrical impedance analysis has not been studied in IBS. Therefore, we designed this exploratory study to assess its potential role in the diagnosis and follow-up of treatment in IBS.

Study Schematic and Schedule of Activities

6.6 Study Schematic

4dFD Four-day Food Diary
BIA Bio-electrical Impedance Analysis
IBS-SSS IBS-Symptom Severity Scale

6.7 Study Activities

	Screening	Visit 1	Subsequent visits (for patients)
Inclusion/exclusion	X		
Informed consent	X		
Rome IV	X		
Clinical parameters		X	X
Intervention type		X	X
Psychological ques-		X	
tionnaires			
IPAQ		X	X
Four Day Food Diary		X	X
BIA		X	X
IBS-SSS		X	X

7 **Study Objectives and endpoints**

7.1 Primary Objective

The primary objective is to compare the BIA parameters including PhA between IBS and healthy individuals.

7.2 Secondary Objectives

The secondary objectives are double:

- Correlation of PhA with different parameters implicated in IBS pathophysiology in IBS patients and healthy subjects.
- Evolution of PhA according to response to therapy.

7.3 Endpoints

The primary endpoint of this study is to explore whether PhA differs between IBS patients and healthy volunteers at visit 1.

The secondary endpoints are multiple and are divided in two parts.

The first part explores correlations at initial presentation among IBS patients and healthy subjects:

- Correlation of PhA with IPAQ
- Multiple regression of IBS status with multiple independent variables (PhA, IPAQ, dietary and FODMAP intake, psychological variables, gender)

In the second part, we want to explore changes of PhA according to changes in IBS-SSS in IBS patients only.

8 Investigational Plan

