9.1 Selection of Study Population

IBS patients will be recruited from the outpatient clinic at the Department of Gastroenterology and Hepatology of UZ Brussels. IBS is defined according to ROME IV criteria. Healthy subjects will be recruited by advertisement.

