10.2.3 IBS status

Presence of IBS will be established based on the ROME IV criteria (appendix 6). IBS will be subtyped according to the predominant stool pattern.

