11.4 Statistical Considerations and Data Analysis

In this explorative study assessing the applicability of BIA as a diagnostic modality or tool for objective evaluation of treatment response, 20 IBS subjects and 20 healthy volunteers will be recruited. Based on the results, a larger study will be considered.

Data collection and analysis will be performed by the study team.

12 Ethical Considerations

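### The primary PhA comparison of clinic patients with advertised volunteers has no matching and no stated adjustment for age or sex, and age is in no planned model

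*Combined protocol and SAP*

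**What the plan says.** The primary endpoint (7.3, repeated in the section 2 summary) reads: "The primary endpoint of this study is to explore whether PhA differs between IBS patients and healthy volunteers at visit 1". It has no test, model or covariate attached. Section 11.4 gives the group sizes, 20 and 20. On analysis it says only: "Data collection and analysis will be performed by the study team". On use of the result it says: "Based on the results, a larger study will be considered".

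Under 9.1, patients are drawn from a hospital gastroenterology outpatient clinic, while "Healthy subjects will be recruited by advertisement". Section 9.2 allows ages 18 to 75 in both groups. The exclusions in 9.3 do not balance age or sex, and no section mentions matching.

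The one multivariable analysis is a secondary endpoint in 7.3: "Multiple regression of IBS status with multiple independent variables (PhA, IPAQ, dietary and FODMAP intake, psychological variables, gender". Gender is in that list and age is not.

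Section 6.1 gives the protocol's own view of the measure: "Phase Angle (PhA) is a new marker for body cell mass and frailty", and "It has been shown to provide insight into the muscle mass in health and disease at different age".

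**The concern.** The two groups are not randomised and come from different sources, so nothing in the design makes their age or sex mix alike. A marker tied to body cell mass, frailty and muscle mass can be expected to vary with age and probably with sex, whether or not a person has IBS. An unadjusted difference then mixes the IBS contrast with whatever demographic difference recruitment happens to produce.

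The error can go either way. A demographic gap may be read as an IBS signal and help to justify a larger study, or it may cancel a real difference and end the line of work.

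**Working it through.** **1. Can the secondary regression stand in for an adjusted primary result?** No, for three reasons.
- Its outcome is IBS status, so it does not give a PhA difference in degrees.
- It omits age.
- It is crowded. The named items PhA, IPAQ, diet, FODMAP and gender make 5. The scales in 10.1.2 (GAD-7, PHQ-9, PHQ-15, VSI) add 4 if each enters separately, giving 9 predictors for 20 patients: 20/9 ≈ 2.2 patients per predictor.

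**2. Size of the bias.** The documents give no PhA SD, age slope or sex difference, so there is no plan figure to reproduce. All of the following are assumptions: women 0.8 deg lower than men; PhA falling 0.01–0.02 deg per year; residual SD 0.6 deg; age SD 12 years; 20 v 20; no true IBS effect; 75% women among patients and 50% among volunteers.

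Unadjusted bias = -(sex effect × gap in proportion of women) - (slope × age gap)
- Sex part: 0.8 × 0.25 = 0.20 deg.
- Age part, nominal 7 years: 0.01 × 7 = 0.07 deg to 0.02 × 7 = 0.14 deg.

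Simulation (6,000–8,000 studies per scenario, ages limited to 18–75, two-sided 5% test) gives:

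| Patients' age relative to volunteers | Unadjusted bias (deg) | False positives | Adjusted for sex only | Adjusted for age and sex |
|---|---|---|---|---|
| 7 years older | -0.27 to -0.33 | 21–28% | -0.07 to -0.13; 6–10% | about 0; about 5% |
| Same age | -0.20 | 13–14% | about 0; about 5% | about 0; about 5% |
| 7 years younger | -0.07 to -0.14 | 6–9% | +0.07 to +0.13; 6–10% | about 0; about 5% |

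Limiting ages to 18–75 shrinks the nominal 7-year gap to about 6.7 years, so the simulated bias can be slightly smaller than the hand sum. With a sex effect of 0.5–1.0 deg and a 7-year gap in either direction, unadjusted bias runs from +0.01 to -0.38 deg and false positives from 5% to 32%.

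**3. Masking.** Take a true difference of -0.5 deg, with 50% women among patients v 75% among volunteers, and patients 7 years younger. By hand, -0.50 + 0.20 + (0.07 to 0.14) = -0.23 to -0.16 deg. Simulated, the unadjusted estimate is -0.17 to -0.23 deg with 11–17% power. Adjusted, it is -0.50 deg with 64% power.

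**4. Check on a different scale.** In SD units, bias = (age–PhA correlation) × (age gap in SDs), and rejection follows a noncentral t with 38 df and noncentrality bias × √(20/2).
- Correlation 0.3, gap 1 SD: bias 0.30 SD, 15.2% false positives.
- Correlation 0.5, gap 1 SD: bias 0.50 SD, 33.8%.
- Correlation 0.2, gap 0.5 SD: bias 0.10 SD, 6.1%.

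Even if both groups came from one source that was 60% female, a gap of 20 points or more in the proportion of women would arise by chance in about 26% of samples of this size.

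**5. Price of adjustment.** Residual df fall from 38 to 36. Unadjusted SE is about √(total variance × 2/20). With 65% women in each group, total variance is 0.36 + 0.8² × 0.65 × 0.35 + (slope × 12)² = 0.52 to 0.56, so SE is 0.23–0.24 deg. Adjusted, it is about 0.6 × √0.1 = 0.19 deg. With a 7-year gap and 75% v 50% women, the adjusted SE is 0.21 deg. With a 20-year gap it is 0.26 deg, against 0.23 deg unadjusted.

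**The case against.** The strongest reply is that silence is not a plan for an unadjusted test. Section 11.4 names no method, and section 6.4 says that relationships with confounding parameters will be assessed, so an adjusted analysis is not ruled out. That is true. But the confounders named in 6.4 are psychological factors, activity and diet. Age appears neither there nor in the covariate list of 7.3, so a reader who follows the text would not adjust for it.

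Second, no section says that PhA differs by sex, and the assumed sex effect and sex gap drive most of the larger figures. This stands as a limit on magnitude. With equal sex mix, patients about 7 years older and a slope of 0.01, the unadjusted bias is only about -0.06 deg and false positives are about 5%.

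Third, bias of about 0 after adjustment follows because the fitted model is the one that generated the data. That also stands. Adjustment removes confounding by age and sex as modelled, and activity, diet, psychological state and BMI may still differ between groups. An adjusted difference would still not prove an effect of IBS.

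Fourth, the study is exploratory. This lowers the stakes, but the result is meant to inform a decision on further work.

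**Conclusion.** The concern holds. That the plan has no matching, no stated covariate for the primary contrast and no age term in any model can be read directly from 7.3, 9.1, 9.2 and 11.4, and it is certain. The size and direction of any bias are not. Under the stated assumptions, the false-positive rate runs from about 5–6% with small or offsetting imbalance to about 30% with larger imbalance, and power for a true 0.5 deg difference can fall from 64% to 11–17%. Because the imbalance cannot be known in advance and the remedy is cheap, this should be fixed before analysis. It does not invalidate the study.

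**What to change.** - In 7.3 and 11.4, define the primary analysis as a linear regression of visit-1 PhA on group, with age (continuous) and sex as covariates. Report the adjusted difference in degrees with its 95% CI, and the unadjusted difference as supportive.
- Add age to the secondary regression.
- Optional: frequency-match volunteers to patients by sex and a broad age band, for example under 45 v 45 and over. This limits the loss of precision if the groups would otherwise differ.
- Minor: section 10.2.3 says "Presence of IBS will be established based on the ROME IV criteria", and with 6.7 and 8.2.1 this implies that Rome IV decides the group. Section 9.2 should state that healthy volunteers do not meet those criteria.

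The cost is protocol wording. Age is already needed for eligibility and gender for the planned regression, so no new data are collected. The statistical price is two degrees of freedom, and a wider SE only if the groups are strongly imbalanced (0.26 v 0.23 deg in the 20-year-gap example).

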9.2 Inclusion Criteria

IBS patients:

- Patients aged 18 75 years;
- Fulfilling the ROME IV criteria for IBS;

For healthy volunteers:

- Patients aged 18 - 75 years;

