9.3 Exclusion Criteria

- Clinical suspicion of an organic disorder different from IBS (patients can be included when this disorder had been excluded);
- Known inflammatory bowel disorder;
- Known major intestinal motility disorder;
- Alcohol (defined as more than 14 U per week) or other substance abuse;
- Active psychiatric disorder;
- Known systemic or auto-immune disorder with implication for the GI system;
- Prior abdominal surgery (with the exception of cholecystectomy or appendectomy);
- Any prior diagnosis of cancer other than basocellular carcinoma;
- Current chemotherapy;
- History of gastro-enteritis in the past 12 weeks;
- Dietary supplements unless taken at a stable dose for more than 12 weeks;
- Treatment with neuromodulators (one neuromodulator taken at a stable dose for more than 12 weeks is allowed);
- Pregnancy.

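### Some patients may reach visit 1 already following IBS diet or exercise advice, so the FODMAP and IPAQ associations with IBS status may partly reflect treatment

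*Combined protocol and SAP*

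**What the plan says.** All references are to the combined protocol and SAP.

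- **Analysis.** Section 7.3 lists "Multiple regression of IBS status with multiple independent variables (PhA, IPAQ, dietary and FODMAP intake, psychological variables, gender") as a secondary endpoint. It is introduced by "The first part explores correlations at initial presentation among IBS patients and healthy subjects". Initial presentation is not defined. The related objective in section 7.2 is "Correlation of PhA with different parameters implicated in IBS pathophysiology in IBS patients and healthy subjects".
- **Standard treatment.** Section 6.1 states that every guideline advises more physical activity in IBS. Section 6.3 says "Current treatment of IBS can be broadly divided into lifestyle modifications, dietary interventions, medical treatment and non-pharmaceutical psychological interventions".
- **Recruitment.** Section 9.1: "IBS patients will be recruited from the outpatient clinic at the Department of Gastroenterology and Hepatology of UZ Brussels". For controls: "Healthy subjects will be recruited by advertisement".
- **Eligibility.** Besides age, the only inclusion criterion for patients in section 9.2 is "Fulfilling the ROME IV criteria for IBS". Among treatments, section 9.3 limits dietary supplements, chemotherapy and neuromodulators, the last as "Treatment with neuromodulators (one neuromodulator taken at a stable dose for more than 12 weeks is allowed"). It has no exclusion, washout or stability rule for a therapeutic diet or an exercise programme.
- **Recording of treatment.** The table in section 6.7 marks an intervention-type item at visit 1 and at later visits. The visit 1 text (sections 8.2.2 and 10.1.2) does not mention it. Section 8.2.3 describes recording the prescribed intervention at subsequent visits only.
- **Visit 1 diary.** Section 8.2.1 places it in the week after the first visit; section 10.1.2 places it in the week before.

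**The concern.** Two predictors of IBS status, FODMAP intake and physical activity, are behaviours that IBS care sets out to change. Volunteers have no reason to receive that advice. If some patients received it before visit 1, part of any group difference in these variables follows from being treated for IBS.

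Diet advice would probably lower recorded FODMAP intake and so create an apparent inverse association with IBS. Exercise advice would probably raise IPAQ scores and could hide a true activity deficit. Section 6.4 treats diet and activity as confounders when PhA is assessed, so their meaning also matters for how PhA is read. Section 11.4 says a larger study will be considered on these results, so an unrecognised artefact could carry forward.

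**Working it through.** **1. Can already-advised patients enter?** Yes. Sections 9.2 and 9.3 contain nothing that would keep them out. Rome IV requires symptom onset at least 6 months earlier (section 6.1; Appendix 6, question 5), which leaves time for earlier advice. Patients on a stable neuromodulator are admitted, so the group is not treatment-naive by design.

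**2. Would the instruments pick the advice up?** Probably. The IPAQ (Appendix 5) covers the last 7 days, and the diary (Appendix 8) asks for normal eating. The diary also asks people not to avoid foods. A patient on a restricted diet could read that either way, so it is likely but not certain that the diary shows the restricted diet.

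**3. Does the plan separate the advised patients?** No. The intervention-type item is not said to cover advice given before visit 1, and no analysis uses it.

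**4. How large could the artefact be?** The plan gives no alpha, SD, effect size or share of treated patients, so it has no figure to reproduce. From the documents: 20 patients and 20 volunteers (section 11.4). Assumed, for illustration: two-sided alpha 0.05, SD 1, no true difference in FODMAP intake, a share q of patients already restricting, and a fall of d SD in those who do.

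Expected spurious difference = −q × d. The rejection rate is from simulated two-sample t-tests, 20 v 20:

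| q | d (SD) | −q × d (SD) | p<0.05 |
|---|---|---|---|
| 0 | – | 0 | about 5% |
| 20% | 0.5 | −0.10 | about 6% |
| 30% | 0.5 | −0.15 | about 8% |
| 50% | 0.5 | −0.25 | about 12% |
| 50% | 1.0 | −0.50 | about 31% |
| 20% | 1.5 | −0.30 | about 13% |
| 30% | 1.5 | −0.45 | about 24% |
| 50% | 1.5 | −0.75 | about 53% |

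This univariate comparison is a gauge only; section 7.3 does not list it. In a logistic regression of IBS status on FODMAP intake alone, q = 50% with d = 1.0 gives a median odds ratio of 0.64 per SD where the true value is 1.

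**5. Does it reach PhA?** Only through correlation. Simulated linear regressions of status on PhA and FODMAP intake, with no true differences and d = 1.5, gave these false-positive rates for PhA:

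- q = 20% to 30%, correlation 0 or 0.2: about 5%
- q = 20% to 30%, correlation 0.4: 6% to 7%
- q = 50%, correlation 0.4: 11%

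The correlations are assumptions too.

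**6. Could the full regression be repeated without advised patients?** Counting PhA, IPAQ, dietary intake, FODMAP intake, four psychological scales and gender gives nine predictors: 20/9 ≈ 2.2 patients per predictor with everyone included. Excluding advised patients leaves 20 × 0.8 = 16 at q = 20% and 20 × 0.5 = 10 at q = 50%, or 1.8 and 1.1 per predictor. That is hardly interpretable.

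**7. Diary timing.** If the diary follows visit 1 (section 8.2.1), even a newly seen patient could record intake after advice given at that visit. If it precedes visit 1 (section 10.1.2), that route is closed. The two sections cannot both apply.

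**The case against.** The strongest reply is that the plan claims no causal direction. Section 7.3 says this part explores correlations, and the pathophysiology wording in section 7.2 describes parameters to be correlated with PhA, not the regression of IBS status. This stands. A reader might infer that the plan mistakes an effect of IBS for its cause; the text does not support that, and what remains is a limit on interpretation.

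A reader might also infer that the cases are known to be established, treated patients. Section 9.1 says only that they come from the outpatient clinic, and initial presentation could be read as early in care. But the phrase is undefined and no criterion enforces it, so the possibility stays open.

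The plan does have an intervention-type item at visit 1, and section 11.4 names no method for any analysis, so failing to use this item is not a singular omission. That is fair. Even so, information on earlier advice that is not collected prospectively may not be recoverable later.

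Finally, the analysis is secondary and exploratory, and with small q and d the artefact is negligible. That limits the weight of the point but does not remove it, because the plan cannot show which case applies.

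**Conclusion.** The concern holds as a possibility that the plan neither prevents nor measures. FODMAP intake and IPAQ at visit 1 may be partly treated values in patients, so their associations with IBS status may be partly a treatment artefact. Within the assumed ranges the false-positive rate for FODMAP intake runs from about 6% (q = 20%, d = 0.5) to about 53% (q = 50%, d = 1.5), against 5% with no advised patients. The documents give neither q nor d, so no point in that range can be singled out.

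A reader might infer that the PhA coefficient is necessarily distorted, or that the primary endpoint is compromised through adjustment. Neither follows. The coefficient moves only if PhA correlates with diet or activity, which the documents do not establish, and the primary PhA comparison is not stated to adjust for these variables.

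The point is worth acting on because the remedy is cheap. It is not a fatal flaw.

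**What to change.** 1. **Record exposure before visit 1, in both groups.** At screening, record any current or previous therapeutic diet, prescribed exercise programme and IBS drug, with start dates. State that the intervention-type item at visit 1 includes earlier advice.
2. **Prespecify one sensitivity analysis.** Repeat the visit 1 PhA comparison and the simple group comparisons of FODMAP intake and IPAQ without already-advised patients. Repeat the full regression only descriptively. Adding treatment as a covariate would not help, because it would nearly coincide with IBS status.
3. **State the interpretation in section 7.3.** The FODMAP and IPAQ coefficients are associations with current, possibly treated, behaviour.
4. **Reconcile sections 8.2.1 and 10.1.2** on when the visit 1 diary is kept. Screening items cannot capture advice given at visit 1 itself.

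FODMAP intake should not be dropped from the model by a rule that depends on how many patients turn out to be advised, since the data would then decide the model's content.

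Cost: a few CRF items, one sentence in section 7.3, and a sensitivity analysis with fewer than 20 patients if any are excluded, and so lower precision. Eligibility and treatment do not change.
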